The results may contribute to improving transfusion practices, enhancing patient safety, improving outcomes, and promoting rational blood use.

Study Type

Non-interventional, cross-sectional observational survey study.

Participants

Physicians working in Hungarian ICUs

Planned number: minimum 100 respondents

Participation is voluntary and anonymous.

Inclusion Criteria

Registered anesthesiology and intensive care residents, trainees, and specialists working in Hungary.

Exclusion Criteria

Anesthesiologists and intensive care practitioners working in non-Hungarian intensive care units.

Funding

No special equipment or financial resources required.

Methods

A descriptive online questionnaire (Google Forms) in Hungarian. No personal or sensitive data are collected. Institutional names are recorded only for geographical analysis. Data collection period: July 1 – September 30, 2025.

Information for Respondents

Dear Colleague,

Transfusion is essential but carries risks. Current evidence supports restrictive strategies. However, Hungarian data on ICU transfusion practices are limited, which is why this survey is conducted.

The questionnaire takes approximately 10–15 minutes. Participation is voluntary and anonymous.

Contact: [contact]

Questionnaire Structure (Summary)

- Type of institution
- Institution and department name
- Years of professional experience
- ICU profile
- Number of ICU beds
- Annual patient volume
- Use of PBM protocol
- Presence of PBM clinic
- Local transfusion protocol
- Transfusion practices (1 vs 2 units)
- Clinical indications
- Hemoglobin thresholds
- Physiological triggers (e.g., lactate, ScvO₂, CO₂ gap)
- Target hemoglobin and physiological values

Endpoints

Primary endpoint:

Use of physiological parameters in transfusion decision-making.

Secondary endpoints:

- Restrictive vs liberal transfusion strategy
- PBM implementation
- Relationship between PBM and transfusion triggers
- Presence of local protocols

Statistical Analysis Plan

Data analyzed using MedCalc software. Results expressed as percentages with 95% confidence intervals. Normality tested with Kolmogorov–Smirnov test. Group comparisons via chi-square test, correlations via Pearson method, and PBM effects via two-way RM ANOVA. Significance: $p < 0.05$.

Publication Policy

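### No adjusted or stratified analysis is specified for the PBM–trigger endpoint, and the RM ANOVA named for PBM is undefined, so centre characteristics cannot be separated from a PBM association

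*Combined protocol and SAP*

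**What the plan says.** Under Endpoints, one of the four secondary endpoints is "Relationship between PBM and transfusion triggers". Study Type describes a one-time observational survey, so PBM exposure is not randomised.

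The Statistical Analysis Plan is one short paragraph. Besides percentages with 95% confidence intervals and a normality test, it lists "Group comparisons via chi-square test", "correlations via Pearson method" and "PBM effects via two-way RM ANOVA", at a 0.05 significance level. It names no regression model, covariate or stratum, and gives no rule for interpreting a PBM association. It does not say what the two ANOVA factors are or what is measured repeatedly.

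Questionnaire Structure (Summary) shows that the relevant background variables are collected: "Type of institution", "Years of professional experience", ICU profile, bed number and annual volume. PBM protocol use and the presence of a PBM clinic are asked separately. On size, the Participants section gives only "Planned number: minimum 100 respondents".

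**The concern.** Whether an ICU has a PBM protocol or clinic is likely to depend on the kind of hospital it is in. So is access to ScvO₂, CO₂ gap or lactate measurement. If both vary with centre size, institution type or ICU profile, PBM and trigger use will be associated across respondents even when PBM makes no difference within comparable centres. None of the methods listed, as described, separates the two explanations.

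This matters because the SAP speaks of PBM effects rather than associations, and the Aim of the Study hopes that the results will help to improve practice. A crude difference reported without a caveat could be taken as support for PBM programmes.

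**Working it through.** **The plan's own figure.** The minimum of 100 respondents comes with no power, effect size, expected rate or precision target, so it cannot be reproduced. For context, the 95% half-width for a proportion of 50% is 1.96 × √(0.5 × 0.5 / 100) = 9.8 percentage points.

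**Inputs.** From the documents: N = 100 and a significance level of 0.05 (taken as two-sided, since sidedness is not stated). Everything else is assumed, because the documents give no rates of PBM or trigger use by type of centre. The assumptions are that 40% of respondents work in large centres, that PBM and trigger use may differ between large and small centres, and that PBM has no effect within either group.

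**Crude comparison, moderate case.** PBM is 50% in large and 20% in small centres; trigger use is 65% and 40%.

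- PBM prevalence: 0.4 × 0.50 + 0.6 × 0.20 = 0.32
- Share in large centres: with PBM 0.20 / 0.32 = 0.625; without PBM 0.20 / 0.68 = 0.294
- Trigger use with PBM: 0.625 × 0.65 + 0.375 × 0.40 = 0.556
- Trigger use without PBM: 0.294 × 0.65 + 0.706 × 0.40 = 0.474
- Crude odds ratio: (0.556 / 0.444) / (0.474 / 0.526) = 1.39, against 1.00 within each centre group

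**Rejection rates.** Surveys were simulated under each scenario (20,000 runs at N = 100, 10,000 at N = 200). Two statistics were compared with 3.84, writing a, b, c, d for the cells of a 2×2 table and n for its total:

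- Crude chi-square: N(ad − bc)² / [(a+b)(c+d)(a+c)(b+d)]
- Cochran–Mantel–Haenszel (CMH), stratified by centre size: [Σ(a − (a+b)(a+c)/n)]² / Σ[(a+b)(c+d)(a+c)(b+d) / (n²(n−1))]

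| Assumed confounding | PBM, large / small | Trigger use, large / small | Crude OR | N = 100: crude vs CMH | N = 200: crude vs CMH |
|---|---|---|---|---|---|
| None | 30% / 30% | 50% / 50% | 1.00 | 5.1% vs 4.9% | 5.0% vs 5.0% |
| Mild | 40% / 25% | 55% / 45% | 1.07 | 5.8% vs 5.3% | 5.4% vs 4.8% |
| Moderate | 50% / 20% | 65% / 40% | 1.39 | 12.2% vs 4.8% | 19.4% vs 5.1% |
| Strong | 60% / 15% | 75% / 35% | 2.22 | 45.9% vs 5.1% | 73.9% vs 4.6% |

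Under moderate or strong confounding, recruiting beyond 100 makes a false-positive result more likely, because the bias stays fixed while its standard error shrinks.

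**Room for covariates.** At about one parameter per 10 events, 20% trigger use in 100 respondents gives 20 events and two parameters: PBM and one other. At 50% use there are 50 events and about five parameters. Institution type and ICU profile may each need several.

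**Sparse tables.** If 10 of 100 respondents had a PBM clinic (assumed), the expected count of trigger users among them would be 10 × 0.20 = 2 at 20% overall use. At 55% use the smallest expected count in that row would be 10 × 0.45 = 4.5. Both are below 5.

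**The case against.** The strongest reply is that the SAP does not assign chi-square to this endpoint. A reader might infer that the PBM–trigger relationship is to be tested by a plain chi-square, but the same sentence assigns PBM effects to the RM ANOVA, and one of its factors could in principle be a centre characteristic. The first part stands: the text does not show that chi-square is the chosen test. The second cannot be credited as adjustment, because the factors are not defined. A natural reading, with PBM status as one factor and the several triggers as the repeated one, leaves no place for a centre variable.

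A reader might also infer that large-centre confounding will produce a PBM association. The documents do not support that. They give no data on how PBM or trigger use varies with centre size, and under the mild scenario the excess false-positive rate is under one percentage point (5.8% against 5%). Nor does the plan say that PBM will be recommended on the strength of this comparison; the favourable remarks on PBM in the Introduction rest on experience in other countries.

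Third, Methods calls the questionnaire descriptive, and a crude association is a valid description if labelled as one. That is correct, but the SAP provides no such label and uses the language of effects.

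Finally, only one secondary endpoint is involved. The primary endpoint, a description of how far physiological parameters are used, is not touched by this point.

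**Conclusion.** The point holds in a limited form. For the PBM–trigger endpoint the plan offers unadjusted methods and an undefined RM ANOVA, and leaves unused the variables that would allow a fairer comparison. Confounding by centre characteristics therefore cannot be separated from a PBM association.

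Its size cannot be fixed from the documents. With no true PBM effect and 100 respondents, the crude chi-square rejects in about 6% to 46% of surveys across the assumed range, and stratifying by size brings this back to about 5%. That correction assumes centre size is the only confounder and is recorded well; in practice some confounding may remain. The finding is a risk of a misleading secondary result. It does not predict that one will occur.

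The view that RM ANOVA is unsuitable rests on the one-time design and on the summary of the questionnaire, in which most items appear categorical. Exact response formats are not given.

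**What to change.** In the Statistical Analysis Plan, for this endpoint:

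1. Replace the RM ANOVA with a logistic regression of trigger use (yes/no, for each trigger) on PBM, adjusted for a small prespecified set. Enter one centre-size or institution-type variable first, then years of experience if events allow, at about one parameter per 10 events. A CMH test stratified by centre size is an acceptable simpler choice.
2. Report the crude odds ratio with its 95% confidence interval beside the adjusted one.
3. For unadjusted 2×2 tables with any expected count below 5, use Fisher's exact test.
4. Describe the results as associations, not PBM effects, and acknowledge residual confounding.

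State whether PBM means the protocol, the clinic or either, and confirm that the named software fits the chosen model. If the change is made after data collection has begun, date it and say so.

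The cost is a few lines of text, one further analysis on variables already collected, and a somewhat wider confidence interval. Standard errors clustered by department are optional. They would require revising the statement in Methods that limits institution names to geographical analysis, so they should not be added without that change.

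### Pearson is the only correlation named and the normality test leads to no alternative, although the numeric survey items are probably skewed, discrete or banded

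*Combined protocol and SAP*

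**What the plan says.** The Statistical Analysis Plan section is one short paragraph. On this point it says "Normality tested with Kolmogorov–Smirnov test", then "Group comparisons via chi-square test", then "correlations via Pearson method", with significance at the 0.05 level. It does not say which variables are tested for normality, which pairs are correlated, or what happens if normality is rejected. No rank-based method appears.

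The questionnaire is given only under "Questionnaire Structure (Summary", as a list of topics without response options. The list mixes:
- nominal items (institution type, ICU profile);
- items that read as yes/no or two-category (PBM protocol, PBM clinic, local protocol, one or two units);
- items that may be numeric or banded (experience, "Number of ICU beds", annual volume, hemoglobin thresholds and targets).

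The design is a "Non-interventional, cross-sectional observational survey study", and the size is stated as "Planned number: minimum 100 respondents".

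**The concern.** Pearson r measures linear association on an interval scale. The candidate numeric items are sizes, counts, or clinical thresholds that respondents tend to give in round steps. Three things can then go wrong. A few very large units can drive the coefficient. The coefficient can be imprecise when both variables are strongly skewed. If an item was collected in three or more bands, r depends on the scores chosen for the bands.

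A normality test would usually be there to switch the method, but this plan names nothing to switch to. For discrete answers the test will almost always reject, and the analyst must then ignore it or choose a method after seeing the data. At stake are the secondary or exploratory associations, such as unit size or experience against hemoglobin threshold.

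**Working it through.** **Inputs.** From the documents: n=100 (the stated minimum) and alpha 0.05. Two-sided testing is assumed because sidedness is not stated. The 100 has no derivation and no coefficient is stated, so there is no plan figure to reproduce. For scale, at n=100 a correlation reaches p<0.05 at |r| = 0.197. All data below are illustrative assumptions.

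**1. Two yes/no items.** Take 60 respondents without a feature (20 positive) and 40 with it (24 positive).

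r = phi = (40×24 − 20×16)/√(60×40×56×44) = 640/2431.8 = 0.263.

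The value is the same with codes 0/1, 1/2 or 0/10, and −0.263 when one item is reversed. It equals √(chi-square/n) = √(6.926/100). There is no coding problem here beyond the sign.

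**2. A four-band item against a yes/no item.** Bands of 40, 30, 20 and 10 respondents have 12, 15, 11 and 5 positives.

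| Band scores | Pearson r | p | n·r² |
|---|---|---|---|
| 1, 2, 3, 4 | 0.182 | 0.070 | 3.30 |
| 2.5, 7.5, 15, 30 | 0.145 | 0.149 | 2.12 |
| 2.5, 10, 20, 35 | 0.160 | 0.111 | 2.57 |
| 0, 5, 10, 20 | 0.161 | 0.111 | 2.58 |
| logs of the second row | 0.195 | 0.051 | 3.82 |

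Spearman is 0.199 (p=0.047) and Kendall tau-b 0.184 under all five scorings. The last column equals the Cochran–Armitage trend chi-square, so a trend test depends on the scores in the same way. If the four categories are nominal, r runs from −0.206 to +0.206 with label order alone and has no meaning.

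**3. One large unit.** There are 99 respondents with unrelated values: beds log-normal with median 10 and log-SD 0.4, and thresholds on six half-gram values from 6.5 to 9 g/dL with probabilities 0.05, 0.40, 0.15, 0.25, 0.10 and 0.05. One respondent with 60 beds and a 9 g/dL threshold is added. Pearson r rises by 0.16 on average and Spearman by 0.03. The share of samples significant is 31% for Pearson and 6% for Spearman.

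**4. Precision with skew.** For log-normal pairs (underlying correlation 0.30, log-SD 1, 4,000 samples) raw Pearson has mean 0.221 and SD 0.134; Spearman has mean 0.284 and SD 0.093. The two estimate different quantities, so SD relative to the mean is the fairer comparison: 0.134/0.221 = 0.61 against 0.093/0.284 = 0.33. The central 95% ranges are 0.01 to 0.52 and 0.10 to 0.46.

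For a skewed volume item against the half-gram thresholds of step 3 (underlying correlation 0.3), power was 0.72 for Pearson and 0.79 for Spearman. This gap depends on the skew assumed. On re-running, it was 0.80 against 0.80 at log-SD 0.4, and 0.65 against 0.79 at log-SD 1.0.

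**5. Type I error.** With independent pairs and no added outlier (20,000 runs), Pearson rejected in 5.1% for thresholds against a yes/no item, 4.8% against a four-level item, 5.1% against log-normal beds, and 4.9% for two log-normal sizes.

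**6. The K-S step.** For the half-gram thresholds, K-S against a fitted normal rejected in 100% of 2,000 samples. It also rejects for a 40/60 binary item (D=0.39, p<0.001) and for the four-band item (D=0.24, p<0.001). This shows that the test is uninformative for such items. It does not show any error in Pearson.

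**The case against.** The strongest reply is that the plan never assigns Pearson to any particular item. It lists no pairs, and it names chi-square separately, which is the natural place for yes/no answers and for the secondary endpoint relating PBM to triggers. Response options are not shown, so experience, beds, volume and hemoglobin values could all be open numeric fields. Pearson's type I error is sound in the ordinary cases of step 5, and no endpoint is tied to a coefficient.

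Most of this stands, and it rules out four stronger readings that a reader might infer:
- *Pearson is prescribed for yes/no, banded or skewed items.* The documents name no variables, and banding and skew are inferences.
- *Every reported correlation depends on arbitrary coding.* For yes/no pairs Pearson is phi. For open numeric items the issue is extreme values and precision. Coding matters only for ordered items with three or more bands, and r is meaningless for nominal items with three or more categories.
- *The p-values are generally invalid.* Step 5 shows otherwise; the 31% in step 3 arises only when an extreme respondent is present.
- *The main result is at risk.* The primary endpoint is reported as a percentage with its 95% CI and needs no correlation.

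The reply does not remove the core. Pearson is the only correlation offered for whatever is correlated, the normality test has no consequence, and a rank method is a better default at almost no cost.

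**Conclusion.** The point holds in this limited form. With Pearson alone and a K-S test that leads nowhere, correlations among the numeric items are exposed to one or two large units, to loss of precision under strong skew and, if bands were used, to the choice of scores.

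On assumed data the size is modest to material. A single extreme respondent raises the significant share from about 5% to 31%. A banded coefficient moves between 0.145 and 0.195. The power loss runs from none under mild skew to 0.65 against 0.79 under strong skew. These figures depend on invented distributions, and confidence that the actual items behave this way is moderate until the response formats are seen. Only secondary or exploratory associations are affected.

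**What to change.** - List the variable pairs to be correlated and the response format of each item.
- Drop the K-S test as a gate.
- For ordered, count or skewed items, report Spearman's coefficient, or Kendall's tau-b where ties are heavy, with a 95% CI.
- For categorical pairs, including PBM against trigger use, report phi or Cramér's V with the chi-square test, and use Fisher's exact test where an expected count is below 5. As an assumed example, 10 respondents with a PBM clinic and 30% trigger use give an expected count of 10 × 0.30 = 3.
- If a trend test or logistic regression is used on banded items, fix the band scores before the data are seen or enter the bands as categories. Otherwise the score dependence of step 2 remains.

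The cost is a few sentences in the analysis plan, with no new data. The only statistical price is a negligible loss of efficiency if a variable proves to be normal.

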It is important to emphasize that the goal of red blood cell transfusion is not solely to normalize hemoglobin levels, but to ensure adequate tissue oxygenation by optimizing oxygen transport capacity. Given the significant heterogeneity of ICU patient populations, individual assessment is essential in all cases. Therefore, a single laboratory parameter—hemoglobin concentration—is insufficient to determine transfusion indication and required dose. In other words, not only the degree of anemia but its consequences determine the need for transfusion.

Assessment should include clinical signs (e.g., general weakness, dizziness, tachycardia, circulatory failure, dyspnea, failed weaning, etc.) and physiological parameters reflecting impaired tissue oxygenation and oxygen deficit/debt (e.g., serum lactate, central venous oxygen saturation, arterio-venous carbon dioxide difference, arterio-venous oxygen content difference).

Patient Blood Management (PBM) focuses on the triad of anemia, blood loss, and transfusion, emphasizing opportunities to modify these factors. Implementation of PBM programs and dedicated outpatient clinics has improved patient safety and reduced blood utilization in many countries. Although Hungary has introduced a National Blood Donation and Blood Saving Program and professional guidelines for managing life-threatening perioperative bleeding, these mainly focus on high-volume bleeding and hemostasis correction. PBM, however, extends beyond this and is also highly relevant in ICU care, even in non-bleeding patients.

The aim of the present questionnaire-based survey is to assess daily transfusion practices in Hungarian ICUs. To our knowledge, no similar survey has previously been conducted in Hungary.

Study Location

Flór Ferenc Hospital, Kistarcsa

Department of Anesthesiology and Intensive Care

[name]

Investigators

[name], PhD – Head of Department, Study Director

[name] – Senior Physician, Investigator

[name] – Senior Physician, Transfusion Responsible, Investigator

[name] – Resident, Co-investigator

Aim of the Study

The aim is to assess transfusion practices in the management of anemic critically ill patients in Hungarian ICUs using an online questionnaire consisting of 15 mandatory and 1 optional question. The study evaluates the use and frequency of physiological transfusion triggers (e.g., serum lactate, ScvO₂, CO₂ gap, oxygen content difference) and the implementation of PBM programs.

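### The repeated-measures ANOVA named for PBM effects does not match a one-time survey, and its outcome, factors and repeated measure are undefined

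*Combined protocol and SAP*

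**What the plan says.** The Statistical Analysis Plan is one short paragraph. For PBM it gives only "PBM effects via two-way RM ANOVA". It does not name the dependent variable, the two factors, the repeated measure or any handling of sphericity. The same paragraph has results presented as percentages with 95% intervals, plans chi-square tests for group comparisons that it does not specify, and plans Pearson correlations.

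The design sections describe a study with one contact per respondent:

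- Study Type: "Non-interventional, cross-sectional observational survey study".
- Participants: "Participation is voluntary and anonymous".
- Methods: "Data collection period: July 1 – September 30, 2025". This section also confines the use of institution names to geographic description.
- Aim of the Study: practice is assessed "using an online questionnaire consisting of 15 mandatory and 1 optional question".

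The endpoint that the ANOVA appears to serve is "Relationship between PBM and transfusion triggers", one of four secondary endpoints. The Questionnaire Structure is a topic list. It has separate items for a PBM protocol and a PBM clinic, several physiological triggers, and "Target hemoglobin and physiological values". Response formats are not given.

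**The concern.** A repeated-measures ANOVA compares means of a quantitative response measured more than once on the same subject. Nothing here is measured over time, responses cannot be linked across occasions, and results are to be proportions. PBM status is a property of the unit, so it can only be a between-respondent factor; the plan does not say what the within-respondent factor would be.

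What is at stake is the PBM and trigger question. An analyst would have to decide, with the answers in view, which items enter, whether the outcome is use, frequency or a cut-off value, and whether PBM means the protocol, the clinic or either. A statistical analysis plan exists to settle such choices beforehand. Even a well-chosen ANOVA would centre on F-tests, whereas readers need an estimate for each trigger of how far its use differs with PBM.

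A smaller matter is the word effects: it reads causally, while the endpoint itself speaks of a relationship, which is all that a cross-sectional survey can show.

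**Working it through.** The plan has no calculation to reproduce on this point. Its only related figure is the minimum of 100 respondents, given without rates, power or a precision target.

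**1. Requirements against the plan**

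| A two-way RM ANOVA needs | The plan provides |
|---|---|
| A named quantitative outcome | None named; results are percentages |
| Two named factors | Neither named; PBM implied as one |
| A measure repeated within respondent | None declared |
| Linkage, if repeated over time | Anonymous, one window, no identifier described |

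**2. If the repeated factor is time.** Occasions per respondent k = 1, so the time factor has k − 1 = 0 degrees of freedom and cannot be fitted.

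**3. If the repeated factor is the trigger item.** Each respondent answers about several triggers, so item could be the within-respondent factor and PBM the between-respondent factor. With n = 100 and an assumed 4 items, the PBM main effect has 1 and n − 2 = 98 degrees of freedom. PBM × item has 4 − 1 = 3 and 98 × 3 = 294.

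This was simulated under no PBM association, with 5,000 runs per setting. Assumptions: yes/no items with baseline use of 80%, 50%, 20% and 5%; a respondent random intercept with SD 1.5 on the logit scale; no clustering by ICU.

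| Assumed PBM share | Type I error, PBM | Type I error, PBM × item |
|---|---|---|
| 10% | 0.055 | 0.052 |
| 20% | 0.049 | 0.048 |
| 50% | 0.051 | 0.048 |

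Monte Carlo standard error: √(0.05 × 0.95 / 5000) = 0.003. All six values agree with 0.05. One administration and binary answers do not by themselves invalidate this form. It does require a common scale: a mean taken across raw lactate, ScvO₂ and CO₂-gap values would have no meaning.

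**4. Clustering, which step 3 leaves out.** Respondents from one ICU share its PBM status. For equal clusters of m respondents with intraclass correlation ρ, the design effect is DE = 1 + (m − 1)ρ, and a nominal 5% test that ignores it has actual error of about 2[1 − Φ(1.96/√DE)]. Both m and ρ are assumptions.

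- m = 3, ρ = 0.1: DE = 1 + 2 × 0.1 = 1.2; 1.96/√1.2 = 1.79; error about 0.07.
- m = 4, ρ = 0.2: DE = 1 + 3 × 0.2 = 1.6; 1.96/√1.6 = 1.55; error about 0.12.

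**5. What a direct comparison can deliver at n = 100.** For trigger use of 50% against 30% (assumed), two-sided 5%, independent respondents:

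power = Φ{[|p₁ − p₂| − 1.96√(p̄(1 − p̄)(1/n₁ + 1/n₂))] / √(p₁(1 − p₁)/n₁ + p₂(1 − p₂)/n₂)}.

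For a 20% PBM share, n₁ = 20, n₂ = 80 and p̄ = 0.34: (0.2 − 1.96 × 0.1184)/0.1230 = −0.26, so power is 0.40. For shares of 10%, 30% and 50% it is 0.26, 0.48 and 0.53. Power of 80% would need about 285 respondents in total at a 20% share, or 186 at 50%. Clustering would raise these numbers. The comparison is therefore best presented as an estimate with its interval.

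**The case against.** The strongest reply is that the plan is under-specified and nothing worse. Repeated measures need not mean time. Several triggers are asked of every respondent, and the Aim of the Study refers to how often they are used, so a common frequency scale is possible. With 0/1 items the mean is the proportion using the trigger, which fits reporting in percentages, and the PBM main effect does not depend on sphericity. The planned chi-square tests could also cover a simple table of PBM against trigger use. The survey is descriptive, and its primary endpoint is untouched.

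Much of this stands, and it rules out three stronger readings that a reader might infer:

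- *That no RM ANOVA could be valid here.* Step 3 shows otherwise for items on one scale. The zero degrees of freedom in step 2 apply only if time is the repeated factor, and the plan does not say that it is.
- *That the answers are all categorical.* Response formats are not shown; haemoglobin thresholds and targets may be numeric.
- *That the PBM endpoint has no usable planned test.* Chi-square may serve, although the plan does not assign it to PBM and it would also ignore clustering.

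The reply does not rescue the sentence itself. The item-based structure is nowhere declared, so adopting it would be a post hoc choice, and it leaves the shared unit-level exposure unaddressed.

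**Conclusion.** The point holds as a mismatch between method and design together with missing specification. It does not show that the PBM question cannot be analysed. The named ANOVA has no repeated occasions to work on, no declared outcome, factors or within-respondent measure, and no allowance for respondents who share an ICU.

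Its reach is one of four secondary endpoints. Its numerical size depends on clustering that the documents do not quantify: about 7% to 12% actual error for a nominal 5% test under the assumptions in step 4, and close to 5% if respondents are effectively independent and same-scale items are used. That the ANOVA is meant for the PBM and trigger endpoint is an inference, since the plan does not map methods to endpoints, but no other endpoint fits it better. The sentence should be corrected before the data are analysed.

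**What to change.** Replace the ANOVA phrase in the Statistical Analysis Plan with:

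> The association of PBM protocol and of PBM clinic (each yes/no) with use of each physiological trigger will be estimated by logistic regression, or by GEE across triggers, and reported as odds ratios with 95% CI and standard errors clustered on institution/department. If the PBM group is small, Fisher exact or Firth-type estimation will be used. Haemoglobin thresholds will be compared by ordinal regression if banded, or by a linear or rank-based method if numeric.

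Also:

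- Write association with PBM in place of PBM effects.
- Amend the Methods sentence on institution names so that they may also be used for clustering.
- State that Fisher exact, if used, does not allow for clustering.

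If the sponsor prefers to keep the ANOVA, it should declare the outcome, the between-respondent factor and the items forming the repeated factor, confirm that they share one scale, and say how clustering is handled.

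Cost: a small text edit, possibly a second software package if MedCalc cannot fit the clustered model, and no new data. Intervals widen by √DE, which is about 10% at DE = 1.2 (√1.2 = 1.10) and 26% at DE = 1.6 (√1.6 = 1.26).
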